1. INTRODUCTION

The purpose of this SAP is to describe the planned analyses for study parts A, B and C to be included in the Clinical Study Report for Protocol 213585. All details of the dose escalation process and associated data review is outlined in the dose escalation plan. Metabolite evaluations will be conducted by DMPK and is not covered in this SAP.

Descriptive study population analyses such as summary of demography and baseline characteristics and additional detail with regards to data handling conventions and the specification of data displays will be provided in the Output and Programming Specification (OPS) document.

1.1. Objectives, Endpoints and Estimands

1.1.1. Objectives and Endpoints

Objectives	Endpoints
Primary Objectives	Primary Endpoints

Part A HV Dose Escalation Single Dose
 
 • To evaluate the safety and tolerability of single escalating oral doses of GSK3915393 administered in the fed state in healthy adult participants 
Part B HV Dose Escalation Repeat Dose
 
 • To evaluate the safety and tolerability of repeat escalating oral doses of GSK3915393 twice daily (BID) administered in the fed and fasted state in healthy adult participants 
Part C CYP3A4 Victim Interaction
 
 • To characterize the PK profile of IV GSK3915393 administered alone and when co-administered with itraconazole in healthy adult participants • To characterize the PK profile of oral GSK3915393 administered 	
Part A and B
 
 • Occurrence of serious adverse events (SAEs), adverse events (AEs) and treatment related AEs • Occurrence of clinically significant changes in physical examination, vital signs, laboratory parameters, and 12-lead electrocardiogram (ECG) findings. 
Part C
 
 • Cmax, tmax, AUC(0-t), AUC (0-∞) and (t_{1/2}) as appropriate

Objectives	Endpoints
alone and when co-administered with grapefruit juice or with itraconazole in healthy adult participants	
Secondary Objectives	Secondary Endpoints

Part A HV Dose Escalation Single Dose
 
 • To characterize the PK profile of single oral doses of GSK3915393 in healthy adult participants • To characterize the PK profile of a single intravenous dose of GSK3915393 in healthy adult participants • To evaluate the safety and tolerability of single microdose doses of GSK3915393 in healthy adult participants 
Part B HV Dose Escalation Repeat Dose
 
 • To characterize the PK profile of single doses and repeat oral doses of GSK3915393 in healthy adult participants 	
Part A
 
 • Maximum observed plasma drug concentration (Cmax), time to maximum observed plasma drug concentration (tmax), area under the plasma drug concentration versus time curve from time zero to last quantifiable concentration (AUC(0-t)), AUC from time zero to infinity (AUC(0-∞)), and apparent terminal half-life (t_{1/2}) as appropriate. • Clearance (CL) and volume of distribution (Vd) following IV administration and absolute bioavailability (F) of oral administration • Fraction of drug escaping hepatic metabolism (F_H) and product of fraction of drug absorbed (F_A) and fraction of drug escaping gut metabolism (F_G) i.e., (F_A*F_G). 
Clinical safety and tolerability data including adverse events (AEs) and serious adverse events (SAEs), clinically significant changes in laboratory values, vital signs and 12 lead electrocardiogram (ECG) readings and physical examinations
 
Part B
 
 • Cmax, tmax, AUC(0-t), and AUC over the dosing interval AUC (0-τ)

Objectives	Endpoints

 • To assess the impact of food on the PK of GSK3915393 in healthy adult participants • To evaluate time to steady-state 	
 • Cmax, tmax and AUC (0-τ) following 1st dose of day • Pre-dose concentrations on Days 2, 3, 5, 7 and 14

Part C CYP3A4 Victim Interaction
 
 • To evaluate the safety and tolerability of a single oral dose of GSK3915393 when administered with grapefruit juice or with itraconazole in healthy adult participants • To evaluate the safety and tolerability of single intravenous dose of GSK3915393 when administered with itraconazole in healthy adult participants • To investigate absorption characteristics and first pass clearance of GSK3915393 	
Part C
 
 • Occurrence of serious adverse events (SAEs), adverse events (AEs) and treatment related AEs • Occurrence of clinically significant changes in physical examination, vital signs, laboratory parameters, and 12-lead electrocardiogram (ECG) findings. • FA, FG and FH
Exploratory Objectives	Exploratory Endpoints

 • To investigate metabolites of GSK3915393 in plasma and urine following oral dosing (Part A and B) • To investigate metabolites of GSK3915393 in duodenal bile following oral dosing (Part B, highest dose only) • To assess potential effect of repeat doses of GSK3915393 on Cytochrome P450 3A4 (CYP3A4) enzyme activity (Part B). • To assess the effect of single dose GSK3915393 on Holter ECG in healthy volunteers. Waveforms will be stored for potential future analysis. 	
 • Metabolites of GSK3915393 in plasma and urine. The analyses will be conducted and reported separately. • Metabolites of GSK3915393 in duodenal bile. The analyses will be conducted and reported separately. • Plasma 4β-hydroxycholesterol to cholesterol ratio at pre-treatment and following repeat dosing of GSK3915393 • If analyses conducted: Centrally read ECG parameters and correlation between plasma levels of GSK3915393 and QTc changes. These analyses if conducted will be detailed in a separate analysis plan.

1.1.2. Estimands

In [Table 2](#), the possible intercurrent events and the rationale for relating them to treatment or otherwise is described. Individual participant data will be included in data listings regardless of the strategies followed for the analyses.

Table 2 Estimands

The following two attributes apply to all estimands:

- Treatment condition: GSK3915393 vs Placebo
- Population: Healthy Volunteers.

Estimand Category	Estimand		
	Variable/Endpoint	Intercurrent Event Strategy	Population Level Summary Measure
Primary Objective (1): To evaluate the safety and tolerability of single escalating oral doses of GSK3915393 administered in the fed state in healthy adult participants.			
Primary 1 (Part A)	
 • Adverse events • Clinically significant changes from baseline in laboratory data • Clinically significant changes from baseline in vital signs • Clinically significant changes from baseline in 12 lead electrocardiograms (ECGs) • Clinically significant changes from baseline in physical examination 	
 • All Intercurrent Events - All data will be reported as captured • (Treatment policy strategy, where we are interested in evaluating all adverse events including clinically significant other safety findings occurring after the start of treatment) 	Descriptive Statistics

[figure not shown]
Estimand Category	Estimand		
	Variable/ Endpoint	Intercurrent Event Strategy	Population Level Summary Measure
Primary Objective (2): To evaluate the safety and tolerability of repeat escalating oral doses of GSK3915393 twice daily (BID) administered in the fed and fasted state in healthy adult participants.			
Primary 2 (Part B)	As defined for Primary Objective 1	As Defined for Primary Objective 1	As Defined Primary for Objective 1
Primary Objective (3): To characterize the PK profile of IV GSK3915393 administered alone and when co-administered with itraconazole in healthy adult participants			
Primary 3 (Part C)	
 • Cmax, • tmax, • AUC(0-t), • AUC(0-∞) and • t_{1/2} 	
 • All Intercurrent Events – a treatment policy approach will be applied such that all available data will be included in analyses. For subjects with partial concentration-time data on a given study period, derived parameters such as AUC will be available on that study period provided there are sufficient concentration data to enable their estimation 	Descriptive statistics Point estimates and 90% CI for ratios of AUC or Cmax for GSK3915393 IV with ITZ vs GSK3915393 IV.
Primary Objective (4): To characterize the PK profile of oral GSK3915393 administered alone and when co-administered with grapefruit juice or with itraconazole in healthy adult participants			
Primary 4 (Part C)	As defined for Primary Objective 3	As Defined for Primary Objective 3	As Defined Primary for Objective 3 Point estimates and 90% CI for ratios of AUC or Cmax for GSK3915393 PO with GFJ vs GSK3915393 PO with water and GSK3915393 PO with ITZ vs GSK3915393 PO with water

Estimand Category	Estimand		
	Variable/ Endpoint	Intercurrent Event Strategy	Population Level Summary Measure
Secondary Objective (1): To characterize the PK profile of single oral doses of GSK3915393 in healthy adult participants			
Secondary 1 (Part A)	
 • AUC (0-∞) • AUC (0-t) • Cmax • t_{max} • t_{1/2} • Absolute bioavailability (F) • F_H • F_A*F_G 	As Defined for Primary Objective 3	Descriptive Statistics
Secondary Objective (2): To characterize the PK profile of single intravenous doses of GSK3915393 in healthy adult participants			
Secondary 2 (Part A)	
 • AUC (0-∞) • AUC (0-t) • Cmax • T_{max} • t_{1/2} • Clearance (CL) (IV only) • Volume of distribution (V_d) (IV only) 	As Defined for Primary Objective 3	Descriptive Statistics
Secondary Objective (3): To evaluate the safety and tolerability of single microdose doses of GSK3915393 in healthy adult participants.			
Secondary 3 (Part A)	As defined for Primary Objective 1	As defined for Primary Objective 1	As defined for Primary Objective 1
Secondary Objective (4): To characterize the PK profile of single doses and repeat oral doses of GSK3915393 in healthy adult participants.			
Secondary 4 (Part B)	
 • AUC (0-24) • AUC over the dosing interval • AUC (0-τ) • Cmax after 1st and 2nd dose 	As defined for Primary Objective 3	Descriptive Statistics Geometric mean & 90% CI for accumulation ratios

Estimand Category	Estimand		
	Variable/ Endpoint	Intercurrent Event Strategy	Population Level Summary Measure
	
 • t_{max} after 1st and 2nd dose • Trough concentrations C_τ • $t_{1/2}$ after 1st dose on day 1 • Accumulation ratios (C_{max} accumulation, R_o) 		
Secondary Objective (5): To access the impact of food on the PK of GSK3915393 in healthy adult participants			
Secondary 5 (Part B)	
 • AUC over the dosing interval • AUC (0-τ) after 1st dose • C_{max} after 1st dose • t_{max} after 1st dose 	As defined for Primary Objective 3	Descriptive statistics Geometric mean ratio and 90% CI for AUC and C _{max} Median difference and 90% CI for t_{max}
Secondary Objective (6): To evaluate time to steady-state			
Secondary 6 (Part B)	
 • Pre-dose concentrations on Days 1-14 (days 2, 3, 5, 7 and 14 only in cohort 1) 	As defined for Primary Objective 3	Descriptive statistics Point estimate and 90% CI for day effect
Secondary Objective (7): To evaluate the safety and tolerability of a single oral dose of GSK3915393 when administered with grapefruit juice or with itraconazole in healthy adult participants			
Secondary 7 (Part C)	As defined for Primary Objective 1	As defined for Primary Objective 1	As defined for Primary Objective 1
Secondary Objective (8): To evaluate the safety and tolerability of single intravenous dose of GSK3915393 when administered with itraconazole in healthy adult participants			
Secondary 8 (Part C)	As defined for Primary Objective 1	As defined for Primary Objective 1	As defined for Primary Objective 1
Secondary Objective (9): To investigate absorption characteristics and first pass clearance of GSK3915393			

[figure not shown]
Estimand Category	Estimand		
	Variable/ Endpoint	Intercurrent Event Strategy	Population Level Summary Measure
Secondary 9 (Part C)	
• F• F_A F_G and F_H	As defined for Primary Objective 3	Descriptive statistics

1.2. Study Design

Overview of Study Design and Key Features

Part C – CYP3A4 Vicitum Interaction

Design Features	
This FTIH study will be a randomized, double-blind, placebo controlled, single center trial in two parts.
 
Part A is a crossover design, single dose (SD), dose escalation study in one cohort of healthy participants. Participants will receive single ascending doses of GSK3915393 or matching placebo as an oral dose in periods 1, 2, 4 and 5 and as a single IV microdose dose in period 3. The initial dosing for all periods in which the dose level has been escalated will be staggered so that 2 participants will be dosed as sentinel participants, one with study drug and one with placebo. After approximately 24 hours, and provided the investigator considers the safety and tolerability of the sentinels to be acceptable, the remainder of the participants scheduled for the period may be dosed. Sentinel dosing is not required in the IV dosing period.
 
Part B is a parallel group, 14-day, repeat oral dose, dose escalation study in 3 cohorts of healthy participants. Participants will receive GSK3915393 or matching placebo BID in each of the sequential cohorts. The initial dosing for all periods in which the dose level has been escalated will be staggered so that 2 participants will be dosed as sentinel participants, one with study drug and one with placebo. After at least 4 days of dosing, and provided the investigator considers the safety and tolerability of the sentinels to be acceptable, the remainder of the participants scheduled for the period may be dosed. The impact of food on the PK of GSK3915393 will be investigated following the

------------------------	--

Overview of Study Design and Key Features	
	
AM dose on three days in all cohort (day 3=fasted, day 5= high fat breakfast, day 7=standard breakfast).
 
The participants, investigator, and study staff are all blinded.
 
Part C is a 5 Single Dose periods in healthy adult participants. In period 1 all participants will receive an IV microdose of GSK3915393. In period 2, all participants will receive an IV microdose of GSK3915393 following prior dosing with itraconazole. In periods 3 and 4, participants will receive oral GSK3915393 with or without grapefruit juice in a randomized crossover design. In period 5, all participants will receive oral GSK3915393 following prior dosing with itraconazole.

Study Intervention	
Part A – Participants will receive GSK3915393 extemporaneous formulations: API filled capsules and placebo capsules according to the treatment sequence to which they are assigned. For the IV dose, participants will receive GSK3915393 at a dose of 100 µg within 24 hours from compounding.
 
Part B – Participants will receive GSK3915393 extemporaneous formulations: API filled capsules and placebo capsules according to the treatment to which they are assigned.
 
Part C – The IV microdose of GSK3915393 will be 100 µg. The oral dose of GSK3915393 to be given in periods 3-5 will be selected after review of the IV PK data from periods 1 and 2 and will not exceed 20 mg. Participants would be either dosed GSK3915393 alone, with grapefruit juice or with itraconazole. Participants will be dosed in the fasted state.

Study Intervention Assignment	
Part A Cohort 1 participants will be randomized to one of the 4 treatment sequences and will receive 1 oral placebo dose and 4 active doses (3 as an oral GSK3915393 dose and 1 as a single GSK3915393 IV microdose):
 
In each cohort in Part B, 9 participants on active versus 3 participants in placebo (i.e., in a 3:1 ratio)
 
In Part C, twelve participants will be randomized to one of the 2 sequences and will receive 2 IV microdose of GSK3915393 and 3

Overview of Study Design and Key Features	
	active oral doses of GSK3915393 either alone, with grapefruit juice or with itraconazole.
Interim Analysis	
The decision to proceed to higher dose strengths in parts A and B will be made by the Data Escalation Committee (DEC) based on assessment of safety, tolerability and pharmacokinetic data at the preceding doses. In part C, an interim evaluation of the pharmacokinetic and safety data in periods 1 and 2 (IV GSK3915393 + ITZ or water) in conjunction with available safety data from parts A and B will be conducted by the DEC to support the selection of the GSK3915393 oral dose to be administered in periods 3-5.
 
The DEC will review blinded outputs which may include individual participant data, tabular summaries, graphical presentations and statistical analysis. GSK members of the DEC may additionally review unblinded data in a GSK only closed session of the DEC. Unblinded data will not be shared with the investigators/site who will remain blinded throughout. Further details are provided in the dose escalation plan.

2. STATISTICAL HYPOTHESES

The primary objectives of parts A and B of this study are to assess the safety and tolerability of single and repeat ascending doses of GSK3915393 in healthy participants and the primary objective of part C is to evaluate the pharmacokinetic interaction between GSK393153 and grapefruit juice and itraconazole.

No formal hypotheses will be tested. However, wherever appropriate, an estimation approach has been used, and point estimates and confidence intervals (CIs) will be constructed.

3. ANALYSIS SETS

For the purposes of analysis, the following analysis sets are defined.

Analysis Set	Definition / Criteria	Analyses Evaluated
Screened	
 • All participants who were screened for eligibility. 	
 • Study Population
Randomised	
 • All participants who were randomly assigned to treatment in the study. • This population will be based on the treatment the participant was randomized to. 	
 • Study Population
Safety	
 • All randomized participants who received at least one dose of study treatment. • This population will be based on the treatment the participant actually received. 	
 • Safety • Study Population
COVID-19	
 • All participants in the Safety set who had a confirmed, probable or suspected COVID-19 case diagnosis. 	
 • Study Population • Safety
Pharmacokinetic (PK)	
 • All participants in the Safety population who had at least 1 non-missing PK assessment. (Non-quantifiable [NQ] values will be considered as non-missing values). • This population will be based on the treatment the participant actually received. 	
 • PK

4. STATISTICAL ANALYSES

4.1. General Considerations

The study population analyses will be based on the Safety set, unless otherwise specified. Safety analyses will also be based on the safety set and PK analyses will be based on the PK set.

4.1.1. General Methodology

Safety evaluations are planned to be descriptive in nature. Statistical modelling will be performed for Pharmacokinetic data, and point estimates with 90% CIs will be constructed.

Unless otherwise specified, summary tables will provide the following descriptive statistics as a minimum:

- Continuous data:
n, mean, standard deviation (SD), median, minimum and maximum.
- Log transformed PK parameters:
n, geometric mean, 95% confidence interval for geometric mean, SD on the log scale (SD (log)), Between subject coefficient of variation (%CVb).
- Categorical data:
number and percentage of participants in each category.

4.1.2. Baseline Definition

Baseline is defined as the last non-missing assessment prior to first dose.

For some ECG and Vital Signs parameters, the pre-dose data is captured as triplicate. In these cases, the baseline will be defined as the mean of the triplicate assessments.

For Part A and B and periods 1, 3 and 4 in part C, the day 1 pre-dosing assessment will be the baseline. However, if there are no pre-dose assessment collected at Day 1, the last available data from either Day -1 or screening (as schedule of assessment in each Cohort permits) will be defined as baseline. If there are no valid assessments from day 1, day -1 or screening, the baseline will be set to missing.

In part A & C, period baselines will be defined utilising the assessments taken in the specific period. Participant level baselines will also be computed and will be the means of the available period level baselines for each participant.

For Part C in periods 2 and 5, the day 1 pre dosing assessment (prior to the day 1 dose of both ITZ and GSK3915393) will be the baseline. However, if this assessment is missing, data collected from days -1 to day -3 will be considered. The closest assessment prior to day 1 pre dose will be set as the baseline. If there are no valid assessments, the baseline will be set to missing.

4.2. Safety Analyses

The primary objective of this study is to evaluate the safety and tolerability of GSK3915393. Safety data will be summarized by dose regimen over time for the safety population set.

4.2.1. Adverse Events Analyses

Adverse events analyses including summaries AEs, SAEs, treatment related AEs and other significant AEs will be based on GSK Core Data Standards.

COVID-19 events will be summarized and listed based on GSK Core Data Standards.

Further details will be provided in the Output Programming Specifications (OPS).

4.2.2. Clinical Laboratory Analyses

Laboratory evaluations including summaries of Chemistry laboratory tests, Haematology laboratory tests, Urinalysis, and Liver function tests will be based on GSK Core Data Standards.

Further details and the potentially clinical important values will be provided in the OPS.

4.2.3. Other Safety Analyses

The summaries of non-laboratory safety test results including vital signs, 12 lead ECG, telemetry, Physical Examination and Pregnancy will be based on GSK Core Data Standards, unless otherwise specified. Further details and the potentially clinical important values will be provided in the OPS.

4.3. Pharmacokinetic Analyses

Part A and B PK analyses planned for the study are a part of the secondary objectives and Part C PK analyses planned for the study is a part of the primary objectives and will be based on the PK set. Data displays will be based on GSK Data Standards and statistical principles. Full details of the planned displays are provided in the OPS.

4.3.1. Pharmacokinetic Parameters

Pharmacokinetic parameters defined in [Table 3](#) will be determined from the GSK3915393 plasma concentration-time data, as data permits. Pharmacokinetic parameters will be calculated using standard non-compartmental analysis and using WinNonlin version 8.0 (or higher).

All calculations of non-compartmental parameters will be based on actual sampling times. For dose escalation meetings nominal sampling times will be used.

Additionally, Itraconazole plasma concentration data collected during Period 2 and 5 in Part C would be summarized separately.

Table 3 Pharmacokinetic Parameters

Parameter	Parameter Description
Part A	
AUC (0-∞)	
Area under the concentration-time curve extrapolated to infinity will be calculated as:
 $AUC(0 - \infty) = AUC(0 - t) + \frac{C(t)}{\lambda_z}$ 
(NOTE: λ_z is the terminal phase rate constant and C(t) is the last quantifiable concentration. % of the extrapolated area should not exceed 20%. Any value of AUC (0-∞) derived with more than 20% extrapolation should be flagged and excluded from summary statistics if >30%).

AUC(0-t)	Area under the concentration-time curve from time zero to the time of the last quantifiable concentration (C(t)) will be calculated using the linear trapezoidal rule for each incremental trapezoid and the loge trapezoidal rule for each decremental trapezoid.
Cmax	Maximum observed concentration, determined directly from the concentration-time data.
tmax	Time to reach Cmax, determined directly from the concentration-time data.
t _{1/2}	Apparent terminal half-life will be calculated as:
	$t_{1/2} = \frac{\ln 2}{\lambda_z}$
CL	The clearance will be calculated as Dose/AUC (0-∞). Calculated only for IV dose regimen.
V _d	Volume of distribution for IV dose regimen.
F	Absolute bioavailability calculated as $[AUC(0-\infty)_{po}/dose_{po}] / [AUC (0-\infty)_{iv} / dose_{iv}]$
F _H	
Fraction of drug escaping hepatic metabolism (F_H) is calculated as $F_H = (1-E_H)$ (E_H = Hepatic extraction ratio)
 
 Where, E_H = CL_{H,b} ÷ Q_{H,b} CL_{H,b} = hepatic blood clearance; Q_{H,b} = hepatic blood flow (1.26 L/h/kg) CL_{H,b} (Dose IV ÷ Plasma AUC(0-inf)) IV ÷ 0.64 (Blood : Plasma)
F _A *F _G	Fraction of drug absorbed intact * Fraction of drug escaping gut metabolism (F _A *F _G) is calculated as $(F_A * F_G) = F \div F_H$

Parameter	Parameter Description
Part B	
AUC (0-10)	Area under the concentration-time dosing interval curve following 1 st dose from time zero to 10 hours post-dose
AUC (10-24)	Area under the concentration-time dosing interval curve following 2 nd dose from 10 hours to 24 hours post-dose.
AUC (0-24)	Area under the concentration-time curve from time zero to 24 hours post-dose.
Cmax 1 st dose	Maximum observed concentration following 1 st dose (0-10h), determined directly from the concentration-time data.
Cmax 2 nd dose	Maximum observed concentration following 2 nd dose (10-24h), determined directly from the concentration-time data.
tmax 1 st dose	Time to reach Cmax following 1 st dose (0-10h), determined directly from the concentration-time data.
tmax 2 nd dose	Time to reach Cmax following 2 nd dose (10-24h), determined directly from the concentration-time data.
Ctrough	Pre-dose concentrations on days 1-14 (days 2 3,5,7 and 14 in cohort 1*)
t _{1/2}	Apparent terminal half-life will be calculated as: $t_{1/2} = \frac{\ln 2}{\lambda_z}$
Cmax accumulation	Cmax accumulation will be calculated as Cmax 1 st Dose _{D7} /Cmax 1 st Dose _{D1}
Ro	Observed accumulations ratio will be calculated as AUC (0-10) _{D7} / AUC(0-10) _{D1}
Part C (CYP3A4 victim assessment)	
Cmax	Maximum observed concentration, determined directly from the concentration-time data.
tmax	Time to reach Cmax, determined directly from the concentration-time data.
AUC(0-t)	Area under the concentration-time curve from time zero to the time of the last quantifiable concentration (C(t)) will be calculated using the linear trapezoidal rule for each incremental trapezoid and the loge trapezoidal rule for each decremental trapezoid.
AUC (0-∞)	Area under the concentration-time curve extrapolated to infinity will be calculated as: $AUC(0 - \infty) = AUC(0 - t) + \frac{C(t)}{\lambda_z}$
t _{1/2}	Apparent terminal half-life will be calculated as:

Parameter	Parameter Description
	$t_{1/2} = \frac{\ln 2}{\lambda_z}$
F_G^1	$F_G = \text{AUC}_{H2O} \div \text{AUC}_{GFJ}$ (oral administration of GSK3915393)
F	Absolute bioavailability calculated as $[\text{AUC}(0-\infty)_{po}/\text{dose}_{po}] / [\text{AUC}(0-\infty)_{iv}/\text{dose}_{iv}]$
F_H	Fraction of drug escaping hepatic metabolism (F_H) is calculated as $F_H = (1-E_H)$ (E_H = Hepatic extraction ratio) 
 Where, $E_H = \text{CL}_{H,b} \div \text{Q}_{H,b}$ $\text{CL}_{H,b}$ = hepatic blood clearance; $\text{Q}_{H,b}$ = hepatic blood flow (1.26 L/h/kg) $\text{CL}_{H,b} (\text{Dose IV} \div \text{Plasma AUC}(0-\text{inf})) \text{ IV} \div 0.64$ (Blood : Plasma)
F_A	$F_A = F \div (F_H * F_G)$
CL	The clearance will be calculated as Dose/AUC (0- ∞). Calculated only for IV dose regimen.

¹ Calculation of F_G assumes that metabolism of GSK3915393 in gut is solely mediated by CYP3A4 and that GFJ inhibits gut but not hepatic CYP3A4. Calculation uses AUC (0- ∞) [or AUC (0-t) or AUC (0- τ) where AUC (0- ∞) cannot be derived].

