#### 4.3.5. IV Microdose in Part A

Predictions of human GSK3915393 PK following IV administration were based on the PBPK model. Human PK estimates derived assuming a weight of 70 kg were; clearance = 72.2 L/h, volume = 106 L.

The IV dose of GSK3915393 to be administered is a microdose of 100 µg, which will be infused over 1 h. The predicted Cmax and AUC(0-inf) have greater than 5000 and 15000-fold safety margins compared with the gender averaged Day 28 Cmax and AUC values observed at the NOAEL in the dog 4 week safety assessment study (Table 4).

A 100 µg total dose of GSK3915393A will be formulated as a 0.1 mg/mL solution (prepared in 20mM Acetate buffer). In an in vitro hemolysis assay using human erythrocytes, GSK3915393 IV Solution for Infusion at concentrations 0.1 mg/mL (prepared in a 20mM acetate buffer) did not produce hemolysis when added to human blood.

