#### **4.3.9. Dose Selection for Part C**

There is a potential of substantial increase in exposure to GSK3915393 following oral administration of GSK3915393 with itraconazole, therefore the interaction of itraconazole will initially be evaluated with an IV micro-dose of GSK3915393 (100  $\mu$ g). This will allow the impact of itraconazole inhibition of hepatic CYP3A4 on systemic exposure to GSK3915393 to be evaluated and inform the selection of the oral dose of GSK3915393 to be administered in periods 3 to 5

Preliminary PK data from Part A of the study showed that following administration of the IV micro-dose (100  $\mu$ g), the observed mean Cmax and AUC values (5 ng/mL and 5

ng.h/mL, respectively) have approximately 1900 and 6800-fold safety margins compared with the gender averaged Day 28 Cmax (9620 ng/mL) and AUC (33900 ng.h/mL) values observed at the NOAEL in the dog 4 week safety assessment study. Therefore there is no risk that the exposures observed in the presence of itraconazole will approach the specified PK stopping criteria.

All available PK data, including information from the IV microdose in the presence of itraconazole will be used to set the oral dose for periods 3-5. The selection of the oral dose will be based on maintaining the predicted exposure to GSK3915393 in the presence of itraconazole in accordance with the defined PK stopping criteria and within the systemic exposures already achieved in Parts A and B of the study and will not exceed 20 mg. See Section 6.5 for further details on dose selection for Part C.

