##### **Study Specific Criteria:**

| AGE   |
|---|
| 1. Between 18 and 50 years of age inclusive, at the time of signing the informed consent.   |
| TYPE OF PARTICIPANT AND DISEASE CHARACTERISTICS   |
| 2. Healthy Participants who are overtly healthy as determined by medical evaluation including medical history, physical examination, laboratory tests, and cardiac monitoring.
3. Negative COVID-19 test on admission. |

|   |
|---|
| WEIGHT  |
| 4. Body weight $\geq$ 40 kg and body mass index (BMI) within the range 18.5-29.9 kg/m  (inclusive).   |
| SEX   |
| 
5. Male or females
 
a. Male participants:
 
 
• No restrictions for male participants.
 
 
b. Female participants:
 
 
• A female participant is eligible to participate if she is not pregnant or breastfeeding, and one of the following conditions applies: 
 
○ Is a woman of non-childbearing potential (WONCBP) as defined in Section 10.4 Contraception and Barrier Guidance.
 
 
 
 
OR
 
 
○ Is a woman of childbearing potential (WOCBP) and using an acceptable contraceptive method as described in Section 10.4 from 30 days prior to first dose until follow up visit. The investigator should evaluate the potential for contraceptive method failure (e.g., noncompliance, recently initiated in relationship to the first dose of study intervention).
 
 
 
• A WOCBP must have a negative highly sensitive pregnancy test (serum) at screening and on admission to the clinical unit, see Section 8.2.6 Pregnancy Testing.
 
• Additional requirements for pregnancy testing during and after study intervention are located in Section 8.2.6. 
 
• The investigator is responsible for review of medical history, menstrual history, and recent sexual activity to decrease the risk for inclusion of a woman with an early undetected pregnancy.
 
 
 
 |

|   |
|---|
| INFORMED CONSENT  |
| 6. Capable of giving signed informed consent which includes compliance with the requirements and restrictions listed in the informed consent form (ICF) and in this protocol. |

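### The hepatic extraction formula divides a clearance in L/h by a blood flow in L/h/kg and never says which body weight reconciles them, so F_H, F_A × F_G and F_A are not properly defined.

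*SAP*

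**What the plan says.** SAP section 4.3.1, Table 3, defines F_H as 1 - E_H, with E_H = CL_H,b ÷ Q_H,b. The two components are:

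- Q_H,b is the "hepatic blood flow (1.26 L/h/kg").
- CL_H,b is ("Dose IV ÷ Plasma AUC(0-inf)) IV ÷ 0.64 (Blood : Plasma").

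The definition appears in the Part A rows and again in the Part C rows. Protocol section 9.4.2 gives the same formula under Part A, and its Part C list refers back to it.

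The numerator is in absolute units. For plasma clearance the SAP says "The clearance will be calculated as Dose/AUC (0"-∞), with no division by weight. The dose is a fixed amount and not an amount per kilogram: "A 100 µg total dose of GSK3915393A will be formulated" (protocol 4.3.5). The protocol's predicted clearance is also absolute, "clearance = 72.2 L/h, volume = 106 L", and is introduced with "Human PK estimates derived assuming a weight of 70 kg were".

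F_H is then a divisor. In Part A, F_A × F_G = F ÷ F_H. In Part C, F_A = F ÷ (F_H × F_G). Neither document multiplies Q_H,b by a weight, normalises clearance by weight, or names the weight to use.

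**The concern.** An extraction ratio must be a pure number between 0 and 1 for F_H to be a fraction. L/h divided by L/h/kg leaves kilograms, so the printed rule does not yield an extraction ratio.

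The per-kilogram unit suggests that weight scaling was intended, but there are two reasonable ways to do it: each participant's own weight, recorded at screening, or the 70 kg on which the protocol's human predictions rest (sections 4.3.1 and 4.3.5). Both give believable values of F_H, and the values differ. A grossly negative F_H would be caught on review. A reasonable-looking F_H from a weight nobody pre-specified would not be, and it would carry into F_A × F_G and F_A.

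**Working it through.** **Plan's own figure.** The documents state no value of E_H or F_H, so there is nothing to reproduce directly. The units of the AUC can be checked. Protocol 4.3.9 reports from Part A "the observed mean Cmax and AUC values (5 ng/mL and 5" ng.h/mL, with an AUC margin of about 6800 against 33900 ng.h/mL. 33900 / 5 = 6780, which agrees, so the AUC is in ng.h/mL.

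**Inputs.** IV dose 100 µg; preliminary mean IV AUC 5 ng.h/mL (protocol 4.3.9); predicted IV AUC 2.14 ng.h/mL (protocol Table 4); blood-to-plasma ratio 0.64; Q_H,b 1.26 L/h/kg; reference weight 70 kg; minimum entry weight 40 kg (protocol 5.1.1).

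**Step 1: as printed.**

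- Plasma CL = 100 µg / 5 ng.h/mL = 20 L/h.
- CL_H,b = 20 / 0.64 = 31.25 L/h.
- E_H = 31.25 / 1.26 = 24.8, so F_H = 1 - 24.8 = -23.8.
- At the predicted AUC: 100 / 2.14 = 46.7 L/h; 46.7 / 0.64 = 73.0 L/h; 73.0 / 1.26 = 57.9; F_H = -56.9.
- A positive F_H would need plasma CL below 1.26 × 0.64 = 0.806 L/h, which is an AUC above 100 / 0.806 = 124 ng.h/mL, about 25 times the preliminary mean.

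**Step 2: scaled by weight W.** E_H = CL_H,b / (1.26 × W). At 70 kg, Q_H,b = 88.2 L/h, E_H = 31.25 / 88.2 = 0.354 and F_H = 0.646.

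**Step 3: own weight against a fixed 70 kg.** The 50 to 90 kg range is my illustration; the documents give no weight distribution. With clearance held at 20 L/h for everyone:

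| Weight | 1.26 × W (L/h) | F_H, own weight | F_H, fixed 70 kg | Shift from using 70 kg |
|---|---|---|---|---|
| 50 kg | 63.0 | 0.504 | 0.646 | +0.14 |
| 70 kg | 88.2 | 0.646 | 0.646 | 0 |
| 90 kg | 113.4 | 0.724 | 0.646 | -0.08 |

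Because F_A × F_G = F ÷ F_H, it changes by 0.504 / 0.646 - 1 = -22% at 50 kg and by 0.724 / 0.646 - 1 = +12% at 90 kg.

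If clearance is instead proportional to weight, own-weight scaling gives 0.646 throughout. A fixed 70 kg gives 1 - (31.25 × 50/70) / 88.2 = 0.747 at 50 kg and 1 - (31.25 × 90/70) / 88.2 = 0.544 at 90 kg, a shift of +0.10 to -0.10.

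**Step 4: does scaling guarantee a valid fraction?** No. At the predicted AUC of 2.14 ng.h/mL and 40 kg, E_H = 73.0 / (1.26 × 40) = 73.0 / 50.4 = 1.45, and F_H is again negative. At the preliminary mean AUC and 40 kg, E_H = 31.25 / 50.4 = 0.62, which is valid.

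**The case against.** The best defence is that the unit is printed. A pharmacokineticist who sees L/h/kg will put both terms on the same basis, and a value such as -23.8 would be stopped at the first output. On that view the text is an incomplete specification, and no reported number is wrong. Section 1 of the SAP also leaves further data-handling detail to the Output and Programming Specification, which is not available here and may name the weight.

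Much of this stands. A reader might infer that the trial is set to report impossible fractions. The documents do not support that: the printed unit points to weight scaling, and no such value appears anywhere. The defence does not supply the missing choice of weight, however, and Table 3 is where the SAP defines the parameter. The F_H rows do not print units for dose or clearance, but the fixed 100 µg dose and the 72.2 L/h prediction leave little doubt that the numerator is absolute. The same omission in two documents and three places makes a text-extraction fault unlikely.

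A reader might also infer that the whole first-pass analysis is compromised. It is not. F is a ratio of dose-normalised AUCs and F_G is a ratio of oral AUCs with water and with grapefruit juice, so neither uses Q_H,b. F_G is also the component that protocol 9.4.3.1 names for predicting lamina propria exposure.

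**Conclusion.** The formula is dimensionally wrong in protocol 9.4.2 and in both Table 3 entries, and the missing weight step has to be supplied. The practical risk is an unspecified choice between two plausible weights. On the illustrative range it is worth +0.14 to -0.08 in F_H with constant clearance, or about +0.10 to -0.10 with clearance proportional to weight.

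These sizes rest on a rounded mean from preliminary data and on an assumed 50 to 90 kg range, so they show scale and do not predict results. The affected quantities are F_H in Parts A and C, F_A × F_G in Part A and F_A in Part C. All are secondary endpoints summarised descriptively. The Part C primary parameters, the AUC and Cmax ratios and the sample-size precision are unaffected.

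**What to change.** In both F_H entries of SAP Table 3 and in protocol 9.4.2, state that Q_H,b = 1.26 L/h/kg × the participant's screening body weight in kg. Dividing CL_H,b by that weight before forming E_H is equivalent. The protocol's Part C definition refers back to Part A and needs no separate edit. Own weight is the natural choice because the flow is given per kilogram and the clearance is individual. If the sponsor prefers 70 kg, the text should say so.

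Add one sentence on values with E_H of 1 or more: for example, that they are listed and flagged, and whether F_H and the quantities derived from it enter the summaries.

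The cost is a few lines of wording in two documents. Weight is already recorded at screening (protocol 1.3 and 8.2.1), so no new data are needed.
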